2.3 Exploratory Objective(s)

- 1. To compare the efficacy of zavegepant to placebo on the mean reduction from the Observation Phase in the number of migraine days per month and number of headache days per month by pain intensity (total; moderate or severe) in each month and over the entire DBT Phase.
- 2. To compare the efficacy of zavegepant to placebo on the proportions of subjects with $\geq 50\%$ reduction, $\geq 75\%$ reduction, and 100% reduction from the Observation Phase in the number of migraine days per month and number of headache days per month by pain intensity (total; moderate or severe) in each month and over the entire DBT Phase.
- 3. To compare the efficacy of zavegepant to placebo on the mean reduction from the Observation Phase in the number of migraine days per week and number of headache days per week by pain intensity (total; moderate or severe) in each week of the first 4 weeks of the DBT Phase.
- 4. To compare the efficacy of zavegepant to placebo on the proportions of subjects with ≥ 50% reduction from the Observation Phase in the number of migraine days per week and number of headache days per week by pain intensity (total; moderate or severe) in each week of the first 4 weeks of the DBT Phase.
- 5. To compare the efficacy of zavegepant to placebo on the proportions of subjects with a migraine day and headache day by pain intensity (total; moderate or severe) on each day of the first week of the DBT Phase.
- 6. To compare the efficacy of zavegepant to placebo on the mean number of acute migrainespecific medication days per month in each month and over the entire DBT Phase.
- 7. To compare the efficacy of zavegepant to placebo on the mean number of acute migraine medication days per month in each month and over the entire DBT Phase.
- 8. To evaluate the frequency of liver function test (LFT) elevations (AST, ALT, or total bilirubin) based on fold changes above ULN in subjects treated with zavegepant during the DBT and OLE Phases.
- 9. To evaluate the frequency of ALT or AST > 3x ULN in temporal association with nausea, vomiting, anorexia, abdominal pain or fatigue in subjects treated with zavegepant during the DBT and OLE Phases.
- 10. To compare the mean changes from baseline in the MSQ preventive role function and emotional function domain scores at Week 12 of the DBT Phase between zavegepant and placebo.
- 11. To compare the mean changes from baseline in the MIDAS absenteeism and presenteeism scores at Week 12 of the DBT Phase between zavegepant and placebo.

- 12. To evaluate the mean changes from baseline in MSQ domain scores and MIDAS scores during the OLE Phase.
- 13. To evaluate the Preference of Medication (PoM) scale during the DBT and OLE Phases.
- 14. To evaluate the Satisfaction with Medication (SM) scale during the DBT and OLE Phases.
- 15. To evaluate the Clinical Global Impression change (CGI-c) scale during the DBT and OLE Phases.
- 16. To evaluate the pharmacokinetics of zavegepant 100 mg and 200 mg.

3 STUDY ENDPOINTS

Migraine days per month and acute migraine-specific medication days per month are derived from eDiary data.

Adverse events (AEs) are determined from case report forms (CRFs).

MSQ domain scores and MIDAS total score are derived from CRFs.

Grade 3 to 4 laboratory test abnormalities are determined from laboratory test values graded using standardized criteria. Laboratory tests are identified from CRFs and central laboratory data.

3.1 Primary Endpoint(s)

Mean change from the Observation Phase in the number of migraine days per month over the entire DBT Phase (Weeks 1 to 12).

3.2 Secondary Endpoint(s)

- 1. Proportion of subjects with $\geq 50\%$ reduction from the Observation Phase in the number of moderate to severe migraine days per month over the entire DBT Phase (Weeks 1 to 12).
- 2. Mean change from the Observation Phase in the number of migraine days per month in the last 4 weeks (Weeks 9 to 12) of the DBT Phase.
- 3. Mean change from the Observation Phase in the number of migraine days per month in the first 4 weeks (Weeks 1 to 4) of the DBT Phase.
- 4. Mean number of acute migraine-specific medication days per month over the entire DBT Phase (Weeks 1 to 12). Acute migraine-specific medications are triptans and ergotamine (see Section 3.3).
- 5. Mean change from baseline in the MSQ restrictive role function domain score at Week 12 of the DBT Phase.
- 6. Mean change from baseline in the MIDAS total score at Week 12 of the DBT Phase.
- 7. Number and percentage of subjects with AEs by intensity, SAEs, AEs leading to study drug discontinuation, and grade 3 to 4 laboratory test abnormalities during the DBT and OLE Phases.
- 8. Number and percentage of subjects with AST or ALT elevations > 3x ULN concurrent (i.e., on the same laboratory collection date) with total bilirubin > 2x ULN during the DBT and OLE Phases.
- 9. Number and percentage of subjects with hepatic-related AEs by intensity, and hepatic-related AEs leading to study drug discontinuation during the DBT and OLE Phases.

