 - b. All subjects must understand the contraception requirements for this study and agree to use 2 acceptable methods of contraception to avoid pregnancy throughout the study in such a manner that the risk of pregnancy is minimized. See Section 5.6 for the definition of WOCBP.
 - c. Women must not be pregnant, lactating, or breastfeeding.
 - d. At the Baseline Visit, prior to dispensing investigational study drug, WOCBP must have a negative pregnancy test.
- 6. Other Inclusion Criteria
 - a. No clinically significant abnormality identified on the medical or laboratory evaluation. A subject with a clinical abnormality or laboratory parameters outside the reference range may be included only if the investigator considers the finding not clinically significant, that it will not introduce additional risk factors, nor interfere with the study assessments of safety or efficacy (not including exclusion criteria listed in Section 5 below).

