8 ADVERSE EVENTS

An Adverse Event (AE) is defined as any new untoward medical occurrence or worsening of a pre-existing medical condition in a subject or clinical investigation subject administered an investigational (medicinal) product and that does not necessarily have a causal relationship with this treatment. An AE can therefore be any unfavorable and unintended sign (including an abnormal laboratory finding, for example) or symptom, or any disease temporally associated with the use of the investigational product, whether or not considered related to the investigational product.

Adverse events can be spontaneously reported or elicited during an open-ended questioning, examination, or evaluation of a subject. In order to prevent reporting bias, subjects should not be questioned regarding the specific occurrence of one or more AEs.

If a specific diagnosis or syndrome is identified by the Investigator, this should be recorded as the AE, rather than recording (as separate AEs) the individual signs/symptoms or clinically significant laboratory abnormalities known to be associated with and considered by the Investigator to be a component of, the disease/syndrome.

Definition of terms related to all Adverse Events (serious and non-serious):

Mild: Is usually transient and may require only minimal treatment or therapeutic intervention. The event does not generally interfere with usual activities of daily living.

Moderate: Is usually alleviated with additional specific therapeutic intervention. The event interferes with usual activities of daily living, causing discomfort, but poses no significant or permanent risk of harm to the subject.

Severe: Interrupts usual activities of daily living, significantly affects clinical status, or may require intensive therapeutic intervention.

Life threatening: An AE is life threatening if the subject was at immediate risk of death from the event as it occurred, i.e., it does not include a reaction that if it had occurred in a more serious form might have caused death. For example, drug-induced hepatitis that resolved without evidence of hepatic failure would not be considered life threatening even though drug-induced hepatitis can be fatal.

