9.3.2 Safety Analyses

Deaths will be listed regardless of onset for the enrolled analysis set.

The frequencies of safety endpoints will be assessed descriptively as the number and percentage of subjects with events/findings separately for the 3 safety analysis sets.

The frequencies of the following safety endpoints will be tabulated on treatment: AEs by intensity (mild, moderate, severe, total); AEs by relationship to study drug (related, possibly related, unlikely related, not related); SAEs; AEs leading to study drug discontinuation; hepatic-related AEs by intensity; hepatic-related AEs leading to study drug discontinuation; clinically significant laboratory test abnormalities; and LFT elevations based on fold changes above ULN, including ALT or AST > 3x ULN concurrent (on the same laboratory test collection date) with total bilirubin > 2x ULN.

The investigators will determine the intensity of AEs and the relationship of AEs to study drug. The investigators' terms will be coded using the latest version of the Medical Dictionary for Regulatory Activities (MedDRA) available at the start of the study. AEs will be tabulated by system organ class and preferred term. In tables by intensity, if a subject has an AE with different intensities over time, then only the greatest intensity will be reported. In tables by relationship to study drug, if a subject has an AE with different relationships over time, then the highest degree of relatedness to study drug will be reported.

Clinically significant laboratory test abnormalities will be identified as grade 3 to 4 laboratory test results graded according to numeric laboratory test criteria in Common Terminology Criteria for Adverse Events (CTCAE) Version 5.0 (2017), if available. Otherwise, if CTCAE grades are not available, then results will be graded according to numeric laboratory test criteria in Division of AIDS (DAIDS) Table for Grading the Severity of Adult and Pediatric Adverse Events Corrected Version 2.1 (2017). If a subject has a laboratory test abnormality with different toxicity grades over time, then only the highest toxicity grade will be reported.

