Removed 'Identity link function, normal distribution'. Changed 'Denominator degrees of freedom method: Kenward-Roger' to 'Standard error (SE) estimation method: Huber-White "sandwich" (refer to the Core SAP)'.

Section 6.3.2.3: Removed text about p-values and hierarchical testing.

Section 6.3.3: Removed Sections 6.3.3.1, 6.3.3.2, 6.3.3.3, 6.3.3.4 and 6.3.3.5.

Section 6.3.3.6: Renumbered to Section 6.3.3.1.

Section 6.3.3.1: Replaced 'reference time point' with 'efficacy data'.

Section 6.3.4: Removed table of plasma zavegepant concentrations along with the text to support this table. Specified that the by-subject plasma zavegepant concentrations will be presented for the DBT efficacy analysis set.

Section 6.4: For On-OL zavegepant for the OL zavegepant safety analysis set, specified to present by OL zavegepant dose and overall. Removed the following: 'OL zavegepant dose and overall, i.e., main presentation', 'Treatment group/OL zavegepant dose and overall, i.e., supplemental presentation'. Removed 'Both presentations are produced'.

Section 6.4.1: Removed 'exposure-adjusted multiple occurrences of unique AEs'.

Section 6.4.1.2: For the AE overview frequency table, removed rows for 'Mild AEs' and 'Moderate AEs', and changed row for 'Severe AEs' to 'Moderate or Severe AEs'.

Section 6.4.1.4: Removed table for exposure-adjusted multiple occurrences of unique AEs along with the calculations.

Section 6.4.1.5: Removed section.

Section 6.4.1.6: Renumbered to Section 6.4.1.5.

New Section 6.4.1.5: Specified to produce the same tables as in Section 6.4.1.4.

Section 6.4.1.7: Removed section.

Section 6.4.1.8: Renumbered to Section 6.4.1.6.

Section 6.4.1.9: Removed section.

Section 6.4.2.1: Removed 'Post-DBT pre-OL zavegepant for the interim safety analysis set' and 'On-DB or OL zavegepant for the DB or OL zavegepant safety analysis set'. Removed tables of laboratory test grade shifts from baseline.

Section 6.4.2.2: Removed bullet: Post-DBT pre-OL zavegepant for the interim safety analysis set. Removed LFT ULN shifts from baseline to worst elevation, exposure-adjusted cumulative LFT elevations, and time to first LFT elevation. Removed LFT plots.

Sections 6.4.2.3 and 6.4.3.1: Removed table of values and changes from DB or OL zavegepant baseline.

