# 6.4.2.1 Laboratory Test Abnormalities

Frequency tables of the worst (highest) laboratory test abnormality for each graded laboratory test are provided for the following safety analysis periods and analysis sets:

- On-DBT for the DBT safety analysis set
- On-OL zavegepant for the OL zavegepant safety analysis set
- Follow-up for the follow-up safety analysis set.

Grade 3 to 4 results support other secondary objective #7.

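### The grade 3 to 4 laboratory count for secondary objective 7 has no baseline condition, so a pre-dose grade 3 to 4 value that persists is tabulated as an on-treatment case

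*Protocol*

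**What the plan says.** Protocol 3.2, item 7, defines the laboratory part of the endpoint as the number and percentage of subjects with "grade 3 to 4 laboratory test abnormalities during the DBT and OLE Phases". Protocol 9.3.2 gives the counting rule: "If a subject has a laboratory test abnormality with different toxicity grades over time, then only the highest toxicity grade will be reported". SAP 6.4.2.1 applies it by period: "Frequency tables of the worst (highest) laboratory test abnormality for each graded laboratory test are provided", separately for on-DBT, on open-label zavegepant and follow-up. It adds that "Grade 3 to 4 results support other secondary objective #7". None of these texts refers to the baseline grade.

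Adverse events serve the same objective but are defined as "any new untoward medical occurrence or worsening of a pre-existing medical condition", so they do carry a new-or-worse condition.

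On entry, Protocol 5.3 sets numeric laboratory limits for eGFR, bilirubin, AST/ALT, neutrophils and HbA1c. For other tests, criterion 6a in Protocol 5.2 says that a subject with a value outside the reference range "may be included only if the investigator considers the finding not clinically significant", with the further provisos that it adds no risk and does not interfere with the assessments.

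**The concern.** A grade 3 to 4 value that was there before the first dose is not an effect of study drug. If it persists, the worst-grade rule still places it in the table that answers secondary objective 7. Two consequences follow.

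- **DBT Phase.** Randomization should spread such carriers evenly over the arms. Adding the same number to each side pulls the ratio for that test toward 1.
- **OLE Phase.** There is no concurrent control. SAP 6.1.1.1 (Table 4) presents the open-label safety set by open-label dose and overall, so subjects who had placebo in the DBT Phase are not shown apart. A value that predates all zavegepant, including one that arose on placebo, reads as a finding on zavegepant.

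The SAP no longer evaluates significance (Section 5), so readers will judge laboratory safety from these percentages directly.

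**Working it through.** **Is there a plan figure to reproduce?** None for this endpoint. The only stated power is at least 90% for the primary endpoint. With 440 v 440 subjects, a 1-day difference, SD 4.2 and two-sided 0.025, it reproduces at 0.9015. It has no bearing here.

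**Step 1: does any output supply the baseline comparison?** SAP 8 says that all outputs described in the SAP are produced, so the list can be checked.

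- SAP 6.4.2.1: worst grade per test and period, with no baseline grade.
- SAP 6.4.2.3: values and changes from baseline for hematology and serum chemistry, with no grades. A handful of subjects among 480 barely moves such a summary.
- SAP 6.4.2 listing: all results over time for subjects with grade 3 to 4 findings. Pretreatment values can be read case by case, but there is no count by arm.
- Grade-shift tables: none in the current text. The revision history (Version 8) records "Removed tables of laboratory test grade shifts from baseline", which confirms that the absence is deliberate.

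**Step 2: which tests are exposed?** Those measured (Protocol 6.2.4.1) without a numeric entry limit (Protocol 5.3), for example CK and lipids. CK is drawn before randomization (Protocol 4.3.1.2) and has no exclusion value. Which tests are graded is left to the Core SAP, so the exposure of CK and lipids assumes that they are graded.

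**Step 3: size in the DBT Phase, for one test.** Let b be the share at grade 3 to 4 before dosing, s the share of those still at grade 3 to 4 on treatment, and q the new-onset risk.

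- Tabulated risk = b·s + (1 − b·s)·q
- Risk difference = (1 − b·s)·(q for zavegepant − q for placebo)

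The documents give none of b, s or q. I assume q = 2% v 1% and vary b·s. Planned arms are 480 per dose and 240 + 240 = 480 pooled placebo.

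| b·s | Carriers per 480 | Zavegepant | Placebo | Difference (points) | Ratio |
|---|---|---|---|---|---|
| 0 | 0 | 2.000% | 1.000% | 1.000 | 2.00 |
| 0.5% | 2.4 | 2.490% | 1.495% | 0.995 | 1.67 |
| 1% | 4.8 | 2.980% | 1.990% | 0.990 | 1.50 |
| 3% | 14.4 | 4.940% | 3.970% | 0.970 | 1.24 |

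For example, at 1%: 0.01 + 0.99 × 0.02 = 2.98% and 0.01 + 0.99 × 0.01 = 1.99%. If only half of the carriers persist, b = 1% gives the 0.5% row. With q = 4% v 2% the ratio falls from 2.00 to 1.66 (b·s = 1%) and 1.39 (3%), while the difference goes from 2.00 to 1.98 and 1.94 points.

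**Step 4: size in the OLE Phase.** The protocol's planning figure is 1200 entrants. Assume 1% carry-over and a 1% new-onset risk. Then 1200 × 1% = 12 carried-over cases and 1188 × 1% ≈ 12 new ones. The tabulated rate is about 2%, twice the new-onset rate, and no control column shows it.

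**The case against.** The case on the other side is substantial.

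- **The Core SAP is not available.** SAP 6.1.2 sends counting rules there, and SAP 6.4.2 sends the graded tests and table contents. It may hold a treatment-emergent rule. This stands: the point concerns what the protocol and SAP say, and SAP 6.4.2.1 cites no such rule.
- **The listing shows each counted subject's history.** With a few carriers per arm, case review is practical. This stands, but a listing does not give a percentage by arm.
- **New laboratory changes also reach the AE tables.** Clinically relevant changes are recorded as AEs (Protocol 6.2.4 and 8.2.2), which must be new or worse. This helps, but depends on investigator judgement, whereas the grade count is numeric.
- **Entry criteria limit carriers.** The numeric limits largely protect liver tests, bilirubin, neutrophils, HbA1c and eGFR, and OLE entrants must meet the laboratory criteria again at Week 12 (Protocol 4.3.3). Protocol 9.3.2 itself calls grade 3 to 4 results clinically significant, which sits badly with admitting one under 6a. This narrows the exposure to tests without a limit; it does not remove it.
- **The study ended early, for business reasons and not a safety concern, and outputs were cut on purpose** (SAP 1). This argues for a small change, not for none.

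A reader might infer that every pre-dose abnormality is counted, or that a drug signal is hidden across the whole endpoint. The documents do not support either. Only values still at grade 3 to 4 on treatment count. The tables are per test, so a persisting CK value cannot dilute an ALT row. Nor is a test weakened: "The frequencies of safety endpoints will be assessed descriptively as the number and percentage of subjects with events/findings". A reader might also take the removal of the shift tables as a contradiction. It is a recorded revision, not an inconsistency.

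**Conclusion.** The point holds in a limited form. As written, the count has no baseline condition, so a grade 3 to 4 value that precedes dosing and persists is tabulated as an on-treatment case. Within the range tried, the ratio for an affected test can fall from 2.00 to between 1.67 and 1.24 (2% v 1% new onset), while the risk difference shrinks by at most 3% of itself. The open-label table is the weaker place, since carried-over values raise its rate with no control to offset them.

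All rates are assumptions and the true size is unknown. The conclusion also assumes that the exposed tests are graded and that the Core SAP has no emergent rule. It concerns how a descriptive table is read, and it is not evidence that a safety signal has been missed.

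**What to change.** In SAP 6.4.2.1, keep the protocol-defined worst-grade count. For each graded test add a second count: grade 3 to 4 on treatment and higher than the baseline grade. Show the two side by side. If the Core SAP already has such a rule, cite it there instead.

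Baseline needs care:

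- **On-DBT:** the pretreatment baseline referred to in SAP 6.2.5.
- **On open-label zavegepant:** the last value before the first dose of any zavegepant. That is the pre-double-blind value for subjects treated with zavegepant in the DBT Phase, and the last value before open-label start for those treated with placebo. SAP 7.1 already derives the matching start date for DB or OL zavegepant.

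Using the last value before open-label start for everyone would be wrong. It would turn an abnormality that arose on double-blind zavegepant into the baseline and drop it from the count.

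Add a footnote with the number of subjects lacking a baseline value. The cost is one extra row per graded test and slightly longer tables, with no new data collection. The added row omits a subject who starts at grade 3, improves and returns to grade 3. Such a subject stays in the protocol-defined row, which is why both are needed.

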3.3 Definition of Migraine Days

A Migraine Day is defined as any calendar day which the subject experiences a qualified migraine headache (onset, continuation or recurrence of the migraine headache). A qualified migraine headache is defined as a migraine with or without aura, lasting for ≥ 30 minutes, and meeting at least one of the following criteria (A and/or B):

- A. ≥ 2 of the following pain features:
 - a. Unilateral location,
 - b. Pulsating quality (throbbing),
 - c. Moderate or severe pain intensity,
 - d. Aggravation by or causing avoidance of routine physical activity (e.g. walking or climbing stairs)
- B. ≥ 1 of the following associated symptoms:
 - a. Nausea and/or vomiting
 - b. Photophobia and phonophobia

During the DBT Phase, if the subject takes an acute migraine-specific medication (i.e., e.g., triptan or ergotamine) during aura or to treat a headache, then it will be counted as a migraine day regardless of the duration and pain features/associated symptoms.

For the full definition of Migraine Days, please refer to Section 17.3 Appendix #3.

3.4 Definition of Headache Days

A Headache Day is any calendar day in which the subject experiences a qualified headache (initial onset, continuation, or recurrence of the headache). A qualified headache is defined as:

- A qualified migraine headache (including an aura-only event that is treated with acute migraine-specific medication), or
- A qualified non-migraine headache, which is a headache that lasts ≥ 30 minutes and is not a qualified migraine headache, or
- A headache of any duration for which acute headache treatment is administered (see Section 5.5.2).
- For the full definition of Headache Days, please refer to Section 17.3 Appendix #3.

4 STUDY PLAN

4.1 Study Design and Duration

This is a multicenter, randomized, double-blind, placebo-controlled study to assess the efficacy and safety of zavegepant in migraine prevention with a 52-week OLE Phase.

The 28-day (+3 days) Observation Phase includes a Screening Visit and a Pre-randomization Laboratory Visit. Note that the +3 days should only be used for scheduling in cases of holidays or weekends. For subjects to be eligible for the study, they must have a one-year history of chronic migraine according to International Classification of Headache Disorders, 3rd Edition, ¹¹ as well as a history of one headache-free day per month during the last 3 months before Screening. Additionally, the subjects must have at least 15 headache days, at least 8 migraine days, and at least 1 headache-free day during 28 days in the Observation Phase which will be documented in the eDiary.

Upon the completion of the Screening Visit, subjects will be provided an electronic diary (eDiary) to document the following on each day of the Observation Phase: migraine occurrence; migraine pain features and associated symptoms (see Section 3.3); and use of acute migraine medication (e.g., triptans; see Section 5.5.2). In addition, subjects will record all concomitant medications, including standard of care migraine medications (both prophylactic and acute), taken in the concomitant medication paper diary (see Sections 5.5.1 and 5.5.2). After completing the Observation Phase, the subject will return to the clinic with the eDiary and concomitant medication paper diary for the Baseline (Randomization) Visit.

Subjects will have blood drawn for baseline laboratory profiles at the Pre-randomization Laboratory Visit; this visit must occur within 96 hours (4 days +2 days) of the Baseline Visit. Note that the +2 days should only be used for scheduling in cases of holidays or weekends. Subjects will then return for the Baseline Visit but cannot be randomized until the pre-randomization laboratory results are reviewed and determined to meet eligibility.

At the Baseline Visit, eligibility for continued participation in the study will be assessed before randomization occurs and study drug will be dispensed. Subjects will be instructed that they must take 4 or 8 soft gelatin capsules (SGC) of blinded study drug every calendar day. If subjects have a migraine during the DBT Phase, they may, if needed, treat the migraine with their standard of care medication and must continue to take study drug.

During the DBT Phase, subjects will record their migraine occurrence, migraine pain features and associated symptoms, and use of acute migraine medication on each day in the eDiary. Subjects will also use the eDiary only during the DBT Phase to complete the Preference of Medication (PoM) questionnaire and the Satisfaction with Medication (SM) questionnaire.

Subjects will also record all concomitant medications, including standard of care migraine medications (both prophylactic and acute), taken during the DBT, OLE, and Follow-up Phases in the concomitant medication paper diary.

At select study visits, subjects will complete or will be administered the Migraine-Specific Quality-of-Life Questionnaire v 2.1 (MSQ v 2.1), the Migraine Disability Assessment (MIDAS), Clinical Global Impression – change (CGI-c) scale, PoM (OLE Phase only), SM (OLE Phase only), and the Columbia-Suicide Severity Rating Scale (C-SSRS) on paper forms.

At the DBT Week 4 and Week 8 Visits, subjects participating in PK draws will be required to dose in person at the study site to assess PK (predose and at least 1 hour after dose; exact time of PK collection relative to the dose will be documented). Additional assessments and visit schedule are outlined in Table 1. Procedures include study personnel review of the eDiary data and concomitant medication paper diary data with the subject, assessment of study drug compliance, and monitoring of tolerability and safety (including collection of adverse events, physical exam, vital signs, laboratory tests, and electrocardiography).

During the Observation Phase, study visits will occur at Screening (Enrollment) and Prerandomization Laboratory.

During the DBT Phase, study visits will occur at Baseline, Week 2, Week 4, Week 8, and Week 12. Subjects who are not eligible to enter the OLE Phase should continue to the Follow-up Phase.

Upon completion of the 12-week DBT Phase, eligible subjects may continue the same dosing regimen (zavegepant 100 mg or 200 mg daily) in the OLE Phase for up to 52 weeks (64 total weeks between DBT Phase and OLE Phase). During the OLE Phase, study visits will occur at Week 14, Week 16, and every 4 weeks thereafter until Week 64. If subjects have a migraine during the OLE Phase, they may, if needed, treat the migraine with their standard of care medication and must continue to take study drug.

During the Follow-up Phase, study visits will occur at Follow-up Week 2 and Follow-up Week 8 for assessment of AEs and laboratory assessments. All randomized subjects should complete the Follow-up Week 2 and Follow-up Week 8 Visits, regardless of completing either treatment phase.

[figure not shown]
To closely monitor for potential drug induced liver injury, guidance on reporting potential drug-induced liver injury (DILI) events is provided in the protocol. Lab results that meet predefined LFT abnormality criteria as DILI should be reported as an SAE. See Section 8.4, Potential Drug Induced Liver Injury (DILI).

Study Schematic

[figure not shown]
Study BHV3500-302 Clinical Protocol, Version 6.0

zavegepant

Study Schematic: Observation, DBT, and Follow-up Phases Figure 1:

Study BHV3500-302 Clinical Protocol, Version 6.0 zavegepant

